# 16.3 Appendix 3: Specific Renal Alert Criteria and Actions and Event Follow-up

Table 16-3 Specific Renal Alert Criteria and Actions

Renal Event	Actions	
Confirmed serum creatinine increase 25 – 49%	

Consider causes and possible interventions

Follow up within 2-5 days

	
Serum creatinine increase 50 % + OR if <18 years old, eGFR < 35 mL/min/1.73 m 	
 
Consider causes and possible interventions
 
Repeat assessment within 24-48h if possible
 
Consider drug interruption or discontinuation unless other causes are diagnosed and corrected
 
Consider patient hospitalization and specialized treatment
 
	
New onset dipstick proteinuria ≥ 3+ OR Protein-creatinine ratio (PCR) ≥ 1g/g Cr (or mg/mmol equivalent as converted by the measuring laboratory)	
 
Consider causes and possible interventions
 
Assess serum albumin & serum total protein
 
Repeat assessment to confirm
 
Consider drug interruption or discontinuation unless other causes are diagnosed and corrected
 
	
New onset hematuria ≥ 3+ on urine dipstick	Assess & document  Repeat assessment to confirm  Distinguish hemoglobinuria from hematuria  Urine sediment microscopy  Assess sCr  Exclude infection, trauma, bleeding from the distal urinary tract/bladder, menstruation  Consider bleeding disorder	

+ Corresponds to KDIGO criteria for Acute Kidney Injury

Additional specialized assessments are available to assess renal function or renal pathology.

(Note: In exceptional cases, when a nephrologist considers a renal biopsy, it is recommended to make slide specimen available for evaluation by the RSG to potentially identify project-wide patterns of nephrotoxicity.)

Whenever a renal event is identified, a detailed patient history and examination are indicated to identify and potentially eliminate risk factors that may have initiated or contributed to the event:

- Blood pressure assessment (after 5-minute rest, with an appropriate cuff size)
- Signs and symptoms like fever, headache, shortness of breath, back or abdominal pain, dysuria or hematuria, dependent or periorbital edema
- Changes in blood pressure, body weight, fluid intake, voiding pattern, or urine output
- Concomitant events or procedures such as trauma, surgical procedures, cardiac or hepatic failure, contrast media or other known nephrotoxin administration, or other diseases or causes, e.g., dehydration due to delirium, tumor lysis

#### Table 16-4 Renal Event Follow Up

#### **FOLLOW-UP OF RENAL EVENTS**

#### Assess, document and record in CRF

- Urine dipstick and sediment microscopy evidence of DIN: crystals, red blood cells (dysmorphic/glomerular vs. non-dysmorphic/non-glomerular), white blood cells, tubular epithelial cells
- Blood pressure and body weight
- Serum creatinine, BUN, electrolytes (sodium, potassium, phosphate, calcium), bicarbonate and uric acid
- Urine output

Review and record possible contributing factors to the renal event (co-medications, other co-morbid conditions) and additional diagnostic procedures (MRI etc.) in the CRF

#### Monitor patient regularly (frequency at investigator's discretion) until -

- Event resolution: (sCr within 10% of baseline or PCR < 1 g/g Cr, or ACR <300 mg/g Cr) or
- Event stabilization: sCr level with ±10% variability over last 6 months or protein-creatinine ratio stabilization at a new level with ±50% variability over last 6 months.
- Analysis of urine markers in samples collected over the course of the DIN event

1.1 Scope of document

The reporting and analysis process (RAP) documents contain detailed information to aid the production of Statistics & Programming input into the Clinical Study Report (CSR) for trial "CQBW251C12201".

The statistical analysis plan (SAP) describes the implementation of the statistical analysis planned in the protocol.

1.2 Study reference documentation

The SAP is developed based on the study protocol v03 dated of 02-Dec-2022.

1.3 Study objectives

Table 1-1 Objectives and related endpoints

Objective(s)	Endpoint(s)		
Primary objective(s)	Endpoint(s) for primary objective(s)		
To assess the change on sputum bacterial colonization	• Change from baseline in bacterial load of colony forming units (CFU/mL, 1 CFU/mL = 1 CFU/g) of potentially pathogenic microorganisms in spontaneous sputum with QBW251 compared to placebo at week 12		
Secondary objective(s)	Endpoint(s) for secondary objective(s)		
To assess the change of QBW251 compared to placebo on sputum bacterial clearance	• Proportion of subjects with absence of any CFU of potentially pathogenic bacteria in sputum culture after 12 weeks of treatment		
To assess the change on patient reported outcomes on bronchiectasis symptom assessment	• Changes from baseline in Quality of Life Questionnaire for Bronchiectasis (QOL-B) (Respiratory symptoms domain) after 12 weeks of treatment.		
To assess the change of fibrinogen plasma concentration	Change from baseline in fibrinogen plasma concentration after 12 weeks of treatment		
To assess the change in rescue medication use	• Change from baseline in rescue medication use (salbutamol/albuterol) after 12 weeks of treatment.		
To assess the change on lung function.	 Changes from baseline in pre- bronchodilator FEV1, FVC after 12 		

Objective(s)	Endpoint(s)		
	weeks treatment, measured by spirometry		
• To assess the change in airway structure and function	 Change from baseline in airway wall and lumen parameters along with extent of global and regional air trapping after 12 weeks of treatment, as measured by HRCT. 		
• To assess the pharmacokinetics of QBW251 in patients with bronchiectasis	• Assessment of drug exposure (Cmax, AUC) and other PK parameters when feasible on Days 1 and 28 (for a subset of patients at selected sites). Pre- and post- dose concentration (Ctrough and Cmax) on Days 1, 28, 56 and 84 (for all patients).		
• To assess the safety and tolerability of QBW251 in patients with bronchiectasis	 All safety endpoints (including adverse events, vital signs, ECG, and safety laboratory changes) during the study 		
Exploratory objective(s)	Endpoint(s) for exploratory objective(s)		
• To examine the change from baseline on sputum bacterial colonization after 12 weeks of treatment with QBW251 compared to placebo and at times of potential exacerbation for assessments of pathogens and bacterial load.	Change from baseline in sputum bacterial colonization after 12 weeks of treatment measured by 16S rRNA PCR		
To assess the change on patient reported outcome	 Changes from baseline in the following PRO after 12 weeks of treatment St. George's Respiratory Questionnaire (SGRQ) Euro Quality of Life-5 Dimensions-3 level (EQ-5D-3L) 		
To explore the effect of QBW251 on additional HRCT outcome measures	 Change from baseline in HRCT endpoints for distribution of mucus (whole lung and regional), airway-artery assessments, and scoring after 12 weeks of treatment 		
To assess the effect of QBW251 on bronchiectasis exacerbation	 Time to first event, Annualized rate of exacerbations as defined by EXACT-PRO questionnaire 		

[figure not shown]
Objective(s)	Endpoint(s)		
To assess the change on biomarkers of inflammation	 Changes from baseline in blood and sputum after 12 weeks of treatment in markers that may include, but are not limited to: Serum hsCRP Blood inflammatory cells e.g. neutrophils, eosinophils Sputum inflammatory proteins e.g. IL-6, IL-8 Serum protein signatures measured by SomaScan (only measured if primary endpoint is positive) 		
 To perform assessment of bacterial species profile in sputum 	 Sputum samples will be biobanked for potential exploration of sputum bacterial profile measured by 16s rRNA gene sequencing 		
To perform DNA assessments to examine whether individual genetic variation in genes relating to drug metabolism and transportation or individual genetic variations in CFTR genes or other disease-relevant genetic pathways confer differential response to QBW251 treatment or correlate with disease severity	Genomic analysis in correlation with exposure to QBW251 or response to QBW251 or disease severity. DNA will be biobanked for potential future analysis of CFTR mutations and for genomic analysis		

1.4 Study design and treatment

This is a randomized, patient- and investigator-blinded, placebo-controlled, parallel-group study investigating the preliminary efficacy and safety of QBW251 administered orally for 12 weeks in participants with bronchiectasis. Approximately 72 participants will be randomized in a 1:1 ratio to receive either QBW251 300 mg b.i.d. or placebo in order to achieve 60 participants who complete the treatment period based on the assumption of a 16% dropout rate. The sample size assumptions will be reviewed in an interim analysis in a blinded manner when approximately 14 participants complete the treatment period.

The study consists of the following periods: Screening, baseline/Day 1, treatment period, and end of study assessments (EOS) visit followed by an additional post-treatment safety follow up via phone call. The total duration for each patient in the study is up to approximately 19 weeks.

The study design is described in Figure 3-1 below.

2 First interpretable results (FIR)

First interpretable results (FIR) will not be provided for this trial due to study termination.

3 Interim analyses

A blinded interim analysis is planned for this study when approximately 14 participants will complete Day 84 post treatment assessment. The purpose of this IA is to confirm sample size assumptions while assessing the variability in bacterial colonization of PPMs in this population. If the variability is larger than the variability assumed originally, a re-estimation/adjustment of the sample size may be applied for the rest of the study.

There will be no pause in enrollment at the time of interim analysis, and subjects may continue to be enrolled until the interim analysis is complete.

All enrolled subjects and the participating investigators will remain blinded during the entire study. Only the sponsor may be unblinded at the interim as necessary.

4 Analysis sets

For all analysis sets, subjects will be analyzed according to the study treatment(s) received.

No screen failure data will be presented.

The Safety Set includes all subjects who received at least one dose of study treatment. The safety set will be used in the analysis of all safety variables.

The PK analysis set will include all subjects with at least one available valid (i.e. not flagged for exclusion) PK concentration measurement, who received any study drug and with no protocol deviations that affect PK data. The PK serial sub-group set will include all subjects

with at least one evaluable drug concentration data sample and who consented to participate in the PK serial sub-group.

The PD analysis set will include all subjects with available PD data at both baseline and at least one post-baseline assessment that are not affected by any protocol deviations.

The analysis sets and protocol deviation codes are related as follows:

Table 4-1 Protocol deviation codes and analysis sets

	-	
Category Deviation code	Text description of deviation	Data exclusion
Subjects are exclu	ded from Safety analysis in case of these PDs:	Exclude subject from Safety analysis set
INCL01	Informed consent was not obtained before any assessment	Υ
Subjects are exclu	Exclude subject from PK analysis set	
INCL01	Informed consent was not obtained before any assessment	Y
OTH07	Patient received incorrect dose	Y
Subjects are exclu	ded from PD analysis in case of these PDs:	Exclude subject from PD analysis sets
INCL01	Informed consent was not obtained before any assessment	Υ

5 Statistical methods for Pharmacokinetic (PK) parameters

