- 2. There was a trend for elevations of the gamma glutamyl transpeptidase to occur more often in patients with higher plasma levels of QBW251 but the interpretation of these findings was limited by the small numbers of patients in each subgroup.
- 3. It was reasonable to dispense with PK monitoring in the ongoing studies and future phase 3 trials of the 300 mg b.i.d. dose as this would not provide more insight into the acceptability of treatment.

Accordingly, Novartis decided to stop further PK threshold monitoring in the present study, though planned PK measurements will continue. The selection of 300 mg b.i.d. as the maximum clinical dose is supported by both the animal chronic toxicology and the clinical study data currently available. The NOAEL dose in the 26-week rat and 39-week monkey chronic toxicology studies was 30 mg/kg/day and 150 mg/kg/day, respectively. Mean systemic exposure (AUC0-24h) at the NOAEL dose was 163,500 ng\*h/mL for the rat at Week 26. For the monkey, the mean exposure (AUC0-24h) at the NOAEL dose (150 mg/kg/day) at Week 39 was 91,700 (range from 52,000 to 159,000) ng\*h/mL. Based on the population PK modeling from COPD DRF study (CQBW251B2201), the mean steady-state daily exposure (AUC0-24h) of QBW251 following 300 mg b.i.d. dose in the COPD patients was 16,460 ng\*h/mL, approximately 5-fold lower than the mean preclinical exposure threshold of 91,700 ng\*h/mL.

The twice-daily dosing regimen was chosen based on the half-life of QBW251 (10-16 hours) and the intent to have a sustained effect on the ion channel. Additionally, a twice daily regimen is expected to provide a reduced Cmax/Ctrough fluctuation compared to once daily dosing. In comparison with a single dosing regimen designed to achieve the same trough concentrations, the proposed twice daily regimen is expected to yield higher average concentrations during the dosing interval. A twice daily regimen was therefore selected to maximize the opportunity of observing efficacy of QBW251 in bronchiectasis patients.

A study duration of 12 weeks is expected to provide clinically significant changes in mucociliary clearance allowing the assessment of safety and tolerability. Moreover, an adequate study duration of at least 3 months is especially important for patient reported outcomes such as quality of life to obtain significant treatment effects.

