5.2 Descriptive analyses

Plasma concentration data for QBW251 will be listed by treatment, subject and sampling time point. Both scheduled and actual times will be included.

Descriptive statistics of QBW251 plasma concentration data will be provided by treatment and visit/sampling time point, including the number and frequency (n, %) of concentrations below the lower limit of quantification (LLOQ), which will be summarized as zero and reported as BLQ in the listing.

Summary statistics of QBW251 plasma concentration data will include mean (arithmetic and geometric), SD, CV (arithmetic and geometric), median, minimum, and maximum. If zero values occur for the values being summarized due to concentrations below the LLOQ, no geometric mean will be calculated.

All PK parameters of QBW251 will be listed by treatment and subject. Summary statistics will be displayed by treatment, using the same summary statistics as for the PK concentrations. An exception to this is Tmax, where only median, minimum and maximum will be presented.

All summaries will be based on the PK analysis set. For all listings displaying individual data, all subjects will be shown, but subjects not in the PK population and values marked as unreliable by the PK Scientist will be flagged.

In addition, the data from this study may be combined with data from other studies and analyzed by means of population modeling and reported separately.

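### SAP Table 4-1 drops a patient from every PK summary for any incorrect dose, although an isolated error can affect at most one PK visit

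*SAP*

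**What the plan says.** To enter the PK analysis set under SAP Section 4, a subject needs "at least one available valid (i.e. not flagged for exclusion) PK concentration measurement". A second condition, on dosing and deviations, limits the set to those "who received any study drug and with no protocol deviations that affect PK data". Protocol Section 12.1 has the same general definition and does not name dosing errors.

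Table 4-1 of the SAP then lists the deviations that count. Code OTH07, "Patient received incorrect dose", is marked Y under "Exclude subject from PK analysis set". The table puts no condition on the timing, size or number of errors. OTH07 does not appear against the safety or PD sets.

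SAP Section 5.2 makes this set decisive for reporting: "All summaries will be based on the PK analysis set". The same section keeps all subjects in the individual listings, where "subjects not in the PK population and values marked as unreliable by the PK Scientist will be flagged". It also allows the data to be pooled with other studies for population modelling.

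The PK serial sub-group set, also in SAP Section 4, requires one evaluable concentration and consent to serial sampling. It states no exclusion for deviations, and Table 4-1 has no row for it.

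**The concern.** The set definition aims at deviations that affect PK data, but Table 4-1 applies that aim to the patient as a whole. A dosing error cannot change a sample drawn before it. For a drug with a half-life of hours, it should also leave no trace at a visit several weeks later. Read literally, one wrong intake in week 2 removes the Day 1 samples, which precede it, and the Day 28, 56 and 84 samples, which follow it by weeks.

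PK is a secondary objective (Protocol Section 2), and only QBW251 patients contribute concentrations (Protocol Section 8.5.2). The planned PK sample is therefore half of the randomized patients, and the SAP says that early termination has left a low sample size (its section on PK/PD relationships). Usable concentrations are being left out of the summaries although the SAP already has a way to set aside single values.

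**Working it through.** The documents give no sample size or precision target for PK, so there is no stated figure to reproduce. The check asks how far an isolated error can reach. Isolated means one incorrect intake with correct dosing resumed at the next dose.

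**Inputs**
- Half-life 10 to 16 h (Protocol Section 4.2).
- PK visits on Days 1, 28, 56 and 84, each with a pre-dose and a 3 h sample (Protocol Section 8.5.2). Table 8-1 allows ±3 days on the last three.
- Serial sampling at 0, 1, 2, 3, 4, 6 and 8 h on Days 1 and 28 (Table 8-1).
- 72 patients randomized 1:1, hence 36 planned on QBW251 (Protocol Section 12.8.1).
- Assumption: linear, first-order kinetics, so the disturbance left after time t is 0.5^(t / half-life).

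**Duration of the disturbance**
- Five half-lives: 5 × 10 = 50 h (2.1 days) to 5 × 16 = 80 h (3.3 days). What then remains is 0.5^5 = 3.1%.
- After 7 days (168 h): 0.5^(168/10) = 0.0009% to 0.5^(168/16) = 0.07%.

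**Distance between visits**
- Nominal gaps are 27, 28 and 28 days.
- The shortest gaps the windows allow are 25 − 1 = 24, 53 − 31 = 22 and 81 − 59 = 22 days.
- Over 22 days (528 h) at 16 h, 528/16 = 33 half-lives pass and 0.5^33 is about 1.2 × 10^-10.
- A 3.3-day disturbance cannot span a gap of at least 22 days, so one isolated error reaches at most one PK visit. Doubling the upper half-life to 32 h gives 5 × 32 = 160 h (6.7 days), and the result is the same.

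**How often it reaches any visit**
- Assumption: the error is equally likely at each of the twice-daily intakes from Day 1 to Day 84, placed on a half-day grid of 2 × 83 + 1 = 167 times, with visits on their nominal days.
- 50 h window: 5 grid times for each of Days 28, 56 and 84 plus one for Day 1 = 16. No visit is affected in 151/167 = 90% of cases.
- 80 h window: 7 × 3 + 1 = 22. No visit is affected in 145/167 = 87% of cases.

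**What is removed**
- Under Table 4-1: all 4 × 2 = 8 sparse samples.
- Under exclusion by sample: 0 to 2 of the 8. A serial-PK patient has 2 × 7 + 2 × 2 = 18 samples and would lose at most 7.

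**Cost per excluded patient**
- 1/36 = 2.8% of the planned QBW251 arm. The standard error of a visit mean grows by a factor √(36/35) = 1.014, about 1.4%. The share is larger if fewer patients contribute, but the number reached before termination is not given.

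**The case against.** The strongest reply is that OTH07 is only a code with a short label, and its specification is not in the documents. The study has one active dose, taken as one capsule twice daily (Protocol Section 6.7.1), so the label could fit a wrong bottle used over a whole dispensing interval as well as one stray capsule. For a sustained error, several visits may be affected and exclusion of the subject is much easier to defend. This stands: the four-visit loss from a trivial error follows from the literal rule, not from any documented case. But the row as written treats both situations alike.

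It can also be said that Table 4-1 does not contradict the set definition, which is itself written by subject. That is fair. The flag on single concentrations in the definition shows that a tool for exclusion by sample exists. It does not show that deviations were meant to be handled that way.

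Three stronger readings are tempting, and the documents do not support them:
- That data are discarded. Excluded patients stay in the listings with a flag, and their values may enter population modelling. Only the summaries lose them.
- That the summaries would describe only perfectly dosed patients and so be biased. Table 4-1 has no PK exclusion for missed doses or interruptions unless these are coded OTH07, and nothing links dosing errors to a patient's kinetics.
- That each case costs 5.0% to 6.7% of the serial data (1/20 to 1/15). This assumes that OTH07 removes patients from the serial summaries, which the serial sub-group definition does not say. It also assumes that half of a target of 30 to 40 optional participants are on QBW251.

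Nor does it harm any planned analysis that these patients remain in the safety and PD sets: the PK/PD analysis has been dropped, and the listings still carry individual exposure.

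**Conclusion.** The point holds as a minor one. OTH07 excludes more than the plan's stated aim requires: for an isolated error all four PK visits leave the summaries, although at most one can be affected.

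The effect is on precision alone, 2.8% of the planned QBW251 arm per excluded patient. SAP Section 5.3 plans no model-based PK analysis, so no test or error rate is involved. If there are no OTH07 cases the effect is nil, and their number is not in the documents.

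The conclusion rests on the stated half-life, on roughly linear kinetics and on the error being isolated. Because visits are at least 22 days apart, it is not sensitive to the exact washout convention. One matter stays open: SAP Section 5.2 ties all summaries to the PK analysis set, while the serial sub-group set has no deviation exclusion. It is therefore unclear whether an OTH07 patient remains in the serial Cmax and AUC summaries.

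**What to change.** Make the change before any PK summary is produced and without reference to the concentrations.

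1. In Table 4-1, and in the matching clause of the PK set definition, turn OTH07 from exclusion of the subject into exclusion of affected concentrations. These are samples drawn from the incorrect dose until about five half-lives (80 h at the upper half-life) after correct dosing resumes. Flag them with the existing value-level mechanism.
2. Keep the patient's other samples in the summaries.
3. Exclude the subject only if no unaffected concentration remains or the dates of the error cannot be established. The Day 1 pre-dose sample precedes all study drug and should not count as the remaining value.
4. State what OTH07 covers, and whether the same rule applies to the PK serial sub-group set.

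The cost is SAP wording plus a short review of dosing dates for each case. Treatment errors go to the dosing CRF (Protocol Section 10.1.5), and the PK listings carry actual sampling times. The date detail on that CRF is not described, and Protocol Section 6.6.1 leaves dose counts in source documents, so some cases may need a site query or fall under the fallback in step 3.
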